# Severity will be determined by study staff. Local reactions will be divided into: 1) mild: events require minimal or no treatment and do not interfere with the patient’s daily activities; 2) moderate: events result in a low level of inconvenience or concern with the therapeutic measures. Moderate events may cause some interference with functioning; 3) severe: events interrupt a patient’s usual daily activity and may require systemic drug therapy or other treatment. Severe events are usually incapacitating. Systemic reaction severity will be based on the World Allergy Organization grading for systemic allergic reactions (mild = grades 1/2, moderate = grade 3, severe = grade 4/5).

\*Will be specified if unexpected, unlisted reaction occurs.

Note: if epinephrine is used, the dose(s) will be recorded in the chart and CRF.

### Total Combined Score

Total Combined Score (TCS) is the sum of the daily symptom scores (DSS) and daily medication scores (DMS) for rhinoconjunctivitis.

Daily Symptom Score (DSS)

	no symptoms = 0	mild symptoms = 1	moderate symptoms = 2	severe symptoms = 3
1. runny nose				
2. stuffy nose				
3. sneezing				
4. itchy nose				
5. gritty/itchy eyes				
6. watery eyes				

Total DSS = \_\_\_\_\_

[figure not shown]
Daily Medication Score (DMS)

	No	Yes	
Did you use an oral antihistamine (Zyrtec) today?			If yes, score = 6
Did you use antihistamine eye drops (olopatadine) today?			If yes, score = 6
Did you use a nasal corticosteroid (Flonase) today?			If yes, score = 8

Total DMS = \_\_\_\_\_

TCS = DSS + DMS = \_\_\_\_\_

### Numeric Rating Scale (NRS) – 11

Instructions for use: The numerical rating scale (NRS) is perhaps the most common pain assessment tool used. It is important to recognize this is an 11-point scale (0-10 not 1-10). Ask the patient whether or not they are experiencing discomfort right now. If so, ask them to describe the discomfort.

To ascertain their understanding of the scale, ask if they would recognize:

- zero is a state of no pain (“0”) (or specific discomfort they describe)
- and the worst pain (or specific discomfort) imaginable (“10”).

Have the patient rate the intensity of their pain/discomfort “right now” verbally with a number or by pointing to the number that represents their pain intensity • This process can be repeated with similar questions about emotional distress

**Patient Global Impression of Improvement (PGI-I)**

Check the box next to the number that best describes how your allergy is now, compared with how it was before you had treatment:		
Very much better	1	
Much better	2	
A little better	3	
No change	4	
A little worse	5	
Much worse	6	
Very much worse	7	

**Selected questions modified from the Patient Experience Questionnaire (PEQ),**

Are you satisfied with the treatment that you received?	( ) Yes	( ) No
Would you recommend the treatment to your friends or family?"	( ) Yes	( ) No

PBO	Placebo
TLF	Tables, listings, and figures
TCS	Total combined score
DSS	Daily symptom score
DMS	Daily medication score
TSS	Total safety score

Statistical Analysis Plan

1. INTRODUCTION

This Statistical Analysis Plan (SAP) describes the planned analysis and reporting for the TX-SMILE study, number TASC-ILIT-MC-2018, an investigator-initiated, multi-center, randomized, double-blind, parallel-group, placebo-controlled study to evaluate the safety, tolerability, and efficacy of an alternative injection site and associated adjustments to dosing and treatment regimen for allergen immunotherapy with a commercially-available, FDA-approved allergenic extract for the immunotherapy treatment of allergic rhinitis and conjunctivitis due to pollen from the conifer Mountain Cedar.

This investigation is a phase 2 proof-of-concept study to evaluate an alternative injection site location (inguinal lymph node versus subcutaneous injection into the upper aspect of the arm) with an associated reduction in the extract dose and number of injections required for treatment of seasonal allergic rhinitis and conjunctivitis due to the conifer Mountain Cedar using an FDA-approved, commercially available product, Mountain Cedar pollen allergenic extract (ALK-Abelló, Inc., Port Washington, NY 11050; US Government License No. 1256).

The structure and content of this SAP is intended to provide sufficient detail to meet the requirements identified by the Food and Drug Administration (FDA) and International Conference on Harmonization of Technical Requirements for Registration of Pharmaceuticals for Human Use (ICH): E9 Guidance on Statistical Principles in Clinical Trials. All work planned and reported for this SAP will follow accepted guidelines and standards, as published by the American Statistical Association.

The following documents were reviewed as the basis for preparation of this SAP;

- Clinical Study Protocol TASC-ILIT-MC-2018
- Case Report Form (CRF) for TASC-ILIT-MC-2018
- ICH E9 Guidance on Statistical Principles for Clinical Trials
- ICH E6 Structure and Content of Clinical Study Reports
- ICMJE Recommendations for Manuscript Preparation
- CONSORT Statement and Checklist for Reporting Clinical Trial Results

The reader of this SAP is encouraged to read the clinical study protocol for additional details on the conduct and operations of the study. Discrepancies between definitions

Statistical Analysis Plan

or explanations between the SAP and protocol will be described. For analytic purposes, definitions in the SAP will prevail.

2. STUDY OBJECTIVE(S), TREATMENTS, AND ENDPOINT(S)

2.1 Study Objective(s)

The TX-Smiles study protocol defined six objectives for the clinical trial, which are as follows:

1. To evaluate the systemic safety of ILIT for Mountain Cedar pollinosis relative to intranodal injections of placebo control based on the proportion of subjects receiving allergenic extract versus the proportion of subjects receiving placebo:
 - 1.1. experiencing anaphylaxis, or
 - 1.2. treated with epinephrine, or
 - 1.3. Experiencing any other treatment-emergent, serious adverse event (SAE) within 60 minutes of the procedure.
2. To evaluate the safety profile of ILIT versus placebo using a standardized scoring system for systemic AEs of interest (AEIs) up to 60 minutes post-procedure
3. To evaluate the efficacy of ILIT relative to placebo during the 2018-2019 Texas Mountain Cedar allergy season as assessed by the daily total combined score (TCS), a composite of the Daily Symptoms Score (DSS) and Daily Medication Score (DMS).
4. To evaluate the tolerability of ILIT using a patient-reported outcome measure
5. To assess the patients' self-reported satisfaction with treatment at the end-of-study.

Statistical Analysis Plan

6. To assess the induction of tolerance to the causative allergen using allergen-specific serum IgE testing

2.2 Treatment Comparisons

2.2.1 Treatment Abbreviations for Data Display

This study included two groups into which patients were randomly allocated in a 1:1 ratio. The active, intralymphatic immunotherapy group, which received a series of three (3) injections of 0.1 mL of the allergenic extract of Mountain Cedar Pollen (ALK-Abelló, Inc., Port Washington, NY 11050; US Government License No. 1256). This group will be denoted as “ILIT” in tables, listings and figures/graphs. ILIT is an abbreviation for “Intralymphatic Immunotherapy”.

The control group in this study was treated with a series of three (3) injections of 0.1 mL of diluent as placebo control, which was sterile saline solution containing 0.4% phenol as a preservative (ALK-Abelló, Inc., Port Washington, NY). This group will be denoted as “PBO” in tables, listings and figures/graphs. PBO is an abbreviation for “placebo.”

2.3 Study Endpoints

The endpoints defined for this study are as follows:

Primary Efficacy Endpoint:

1. Average daily TCS during the 2018-2019 Mountain Cedar pollen season

Secondary Efficacy Endpoints:

Statistical Analysis Plan

1. Proportion of days during pollen season for which active patients experience a lower TCS than placebo patients
2. Patient reported pain or discomfort immediately after and 30 minutes post ILIT procedure
3. Patient-reported treatment satisfaction at the end of the study
4. Reduction in skin reactivity assessed using allergenic-specific serum IgE testing from pre-treatment to post-treatment (the end-of-study visit)

Exploratory Endpoints:

1. Use of rescue inhalers by patients with stable asthma

Safety Endpoints:

1. Proportion of subjects experiencing a serious, treatment-emergent AE up to 60 minutes after an intranodal injection procedure
2. Proportion of subjects experiencing systemic reactions to ILIT relative to placebo and severity of reactions relative to placebo as assessed by the Total Safety Score (TSS)
3. Proportion of subjects reporting local injection site reactions relative to placebo and severity of local reactions relative to placebo, as assessed by the TSS

4. STUDY DESIGN

TASC-ILIT-MC-2018 is a randomized, double-blind, parallel-group, placebo-controlled study.

5. SAMPLE SIZE CONSIDERATIONS

5.1. Significance Level and Power

To determine sample size, the following were assumed:

Statistical Analysis Plan

- Tests will be two-sided and performed at the $\alpha = 0.05$ significance threshold
 - Study participants will complete the diary assessments (DSS, DMS) to yield a daily TCS on at least 50% of the possible days during the allergy season
 - The difference between the average daily TCS for the placebo group and the ILIT group will 8.0 with an assumption that the standard deviation of the average daily TCS is 9.0 across both groups
 - The randomization will be 1:1
 - Using a priori sample size for multiple linear regression with an effect size 0.50 (f^2) for the active treatment group
 - The screen failure rate is estimated to be approximately 12%
-
- A total of 26 screened patients will be required to enroll a total of 23 subjects into this two-treatment parallel-design study (up to 16 per group), the probability is 80% that the study will detect a treatment difference at a two-sided 0.05 significance level, if the true difference between treatments is a 0.50 effect size under multiple linear regression with two predictors (Soper, D.S. (2018). A-priori Sample Size Calculator for Multiple Regression [Software]. Available from <http://www.danielsoper.com/statcalc>).

5.2. Definition of Clinical Relevance

The total symptom score (TCS) is the primary efficacy endpoint and a composite of the DSS and DMS for the peak allergy season, following the method of Blaiss and colleagues (Blaiss et al., 2010). This approach is consistent with EAAAI (Pfaar et al., 2014), FDA (Guideline Allergic Rhinitis: Developing Drug Products for Treatment Guidance for Industry, Draft Guidance Feb 2016), and WAO recommendations for use of an integrated efficacy assessment of both symptoms and medication usage. The advantages and disadvantages of the total combined score approach are outlined in Pfaar et al 2014, the EAAAI position paper on the development of allergy treatments. This tool integrates well characterized and validated symptoms measures of rhinoconjunctivitis on a 0-3 point scale where 0 = no symptoms; 1 = mild symptoms (sign/symptom clearly present, but minimal awareness; easily tolerated); 2 = moderate symptoms (definite awareness of sign/symptom that is bothersome but tolerable); and, 3 = severe symptoms (sign/symptom that is hard to tolerate; causes interference with activities of daily living and/or sleeping). By integrating this with measures of rescue

Statistical Analysis Plan

medication use, the combined burden of symptoms and treatment are calculated. Previous studies have reported differences in the TCS in the range of 1 to 8 units. A difference of 1 on the TCS corresponds to reducing a single mild symptom to absent, while a difference of 6 corresponds to not needing a daily anti-histamine or the complete reduction of two symptoms from severe to not present. A large pivotal study by Blaiss et al., formed the basis for approval of oral grass pollen immunotherapy based on a 1.5 point difference on the TCS between active and placebo groups at a significance level of $p = 0.001$.

6. ANALYSIS POPULATIONS

The populations as defined below were used in study summaries and analyses.

Intent-to-Treat (ITT) Analysis Dataset: will include all consented participants and be used for subject listings and demographics tables.

Modified Intention-to-Treat (MITT) Analysis Dataset: will include all consented participants who received at least one (1) study intervention (intralymphatic injection) and completed at least one (1) complete daily e-diary assessment and be used for production of efficacy tables, subject listings, and demographics tables.

Safety Analysis Dataset: will include all participants who took received at least one (1) dose of study intervention (intralymphatic injection) regardless of whether they provided any diary data and will be used for safety tables and tolerability tables.

Per-Protocol (PP) Analysis Dataset: will include the subset of participants in the MITT data set who received three study treatment injections and completed at least one e-diary responses during the allergy season (defined below), and had no other major protocol violations, and will be used for production of supplementary efficacy tables and analyses.

Additional exploratory datasets for sub-populations and post hoc analysis will include the adjusted per protocol dataset (aPP-IgE) for baseline serum IgE, which is the PP dataset subset of patients with baseline levels of mountain cedar-specific serum IgE greater than 0.3 (definitively positive) and the aPP subset for controlled asthma (aPP-A), if there are sufficient numbers of patients with confirmed, controlled asthma at baseline.

The mountain cedar pollen season will be defined from the first date of a mountain cedar pollen count greater than or equal to 100 ppm thru the date with a pollen

Statistical Analysis Plan

count greater than or equal to 100 ppm followed by five consecutive days with a pollen count below 100 ppm during the Winter 2018-2019 mountain cedar pollen season in Central Texas.

6. CONSIDERATIONS FOR DATA ANALYSIS

6.1 Programming Environment

Data analysis will be conducted in R Studio version 1.1.456 and Python 3.7 using Spyder 3.3.3. Both systems will be run inside Anaconda Navigator.

6.2 Multicenter Studies

Although originally planned as a multicenter study to accommodate the possibility that pollen counts would vary significantly between areas, all patients were enrolled from the Austin, Texas area at the Austin, Texas site, site 001. Because this was a single-center study, no by site analysis will be conducted.

6.3 Strata and Covariates

The primary efficacy analyses on the daily symptom and medication scores (DSS, DMS) and Total Combined score will be examined in relation to the baseline Mountain Cedar-specific serum IgE level as an explanatory covariate using either a linear mixed model or stratified into low and high baseline serum IgE immunoreactive groups.

6.4 Subgroups

There are two potential subgroups of interest. The first subgroup of interest is subjects with controlled asthma identified in their baseline medical history. The second subgroup of interest is patients with other allergies identified in their baseline medical history. In both cases, it is anticipated that there will be few subjects enrolled and thus statistical tests will not be performed on subgroups due to small number of expected subjects. However, if there are sufficient numbers patients enrolled in the study across both treatment arms, subgroups will be examined for exploratory analysis.

Subgroup analyses for efficacy and safety may be conducted for dichotomized sub-groups based on sex (M/F) and age (18-65 years versus / >65 years). Sub-

Statistical Analysis Plan

group analysis will be exploratory. Identification of additional co-variates and use of additional co-variates in regression models will be considered exploratory.

6.6 Significance level

For prespecified analysis, a significance level of $p < 0.05$ will be used. However, as an exploratory, proof-of-concept study, p-values will be reported for parametric and non-parametric tests.

6.7 Multiplicity

There is a single primary endpoint, with a single primary hypothesis test, so no adjustment for multiplicity is needed for the primary endpoint.

To adjust for multiplicity among the secondary endpoints, a fixed testing order will be used. The secondary endpoints will be tested in the pre-specified order, if the primary endpoint is found to be statistically significant. Testing will proceed to the next endpoint if the preceding endpoint is found to be statistically significant at the 5% (two-sided) level. The moment an endpoint is found not to be significant at the 5% (two-sided) level, all remaining endpoints will be considered exploratory, instead of confirmatory. No adjustment for multiplicity will be made for the exploratory endpoints.

The Holm-Bonferroni correction will be used for pre-specified multiple comparisons due to correlation between endpoints based on the TCS.

7. DATA HANDLING METHODS

7.1 Missing Data

No imputations for missing days of diary.

7.2 Premature Discontinuation

Not applicable.

7.3 Visit Windows

Visit windows and checks are based on the following table:

Statistical Analysis Plan

Screening Visit	Treatment Visit 1 ^c	Treatment Visit 2	Treatment Visit 3	Patient Diary	End-of-Study Visit 4
Day -21 to Day 1	Day 1	Day 28 +/-3	Day 56 +/-6	Approx. Dec 2018 to March 2019	March – April 2019

7.4 Data Derivations

The following derivations will be made to produce analysis datasets.

- 1) Age at enrollment = Date of Enrollment – Date of birth
- 2) Total Combined Score: see below
- 3) Cumulative Safety Score: See below

Total Combined Score (TCS) is the sum of the daily symptom scores (DSS) and daily medication scores (DMS) for rhinoconjunctivitis. TCS will be calculated for each patient on each day that a diary result is available.

Daily Symptom Score (DSS) is derived from the patient diary according to the following rubric.

	no symptoms = 0	mild symptoms = 1	moderate symptoms = 2	severe symptoms = 3
1. runny nose				
2. stuffy nose				
3. sneezing				
4. itchy nose				
5. gritty/itchy eyes				
6. watery eyes				

Statistical Analysis Plan

Total DSS = Sum of individual symptoms scores.

Daily Medication Score (DMS) is derived from the patient diary according to the following rubric.

	No	Yes	
Did you use an oral antihistamine (Zyrtec) today?			If yes, score = 6
Dis you use antihistamine eye drops (olopatadine) today?			If yes, score = 6
Did you use a nasal corticosteroid (Flonase) today?			If yes, score = 8

Total DMS = Sum of scores for medical use reported on each day.

Thus, for each patient on each day during the allergy season is $TCS = DSS + DMS$. Since all patients were instructed to take a daily oral anti-histamine, the expected lower-bound for the TCS is a score of 6.

Total Safety Score – Each patient will receive a calculated Safety Score at each Treatment Visit (1, 2, and 3) based on the key below. A cumulative Safety Score for each patient will be calculated from the sum of the Safety Score at each visit. The Total Safety Score for a treatment group will be the sum of the cumulate Safety Score for each patient in the assigned group (ILIT or PBO).

Statistical Analysis Plan

Subject ID:

Injection # (write in 1, 2, or 3):

RECORDING INSTRUCTIONS: Mark/code the box(es) indicating reactions experienced by this subject following injection (D = definitely related to study, P = probably related to study, N = not related to study)

ILIT protocol defined grading scale for severity# of adverse events			
	Mild	Moderate	Severe
LOCAL REACTIONS			
Lymph node swelling			
Itch			
Redness			
Other*			
SYSTEMIC REACTIONS			
Rhinorrhea			
Sneezing			
Dyspnea			
Cough			
Wheeze			
Pruritus			
Rash			
Angioedema			
Nausea			
Vomiting			
Diarrhea			
Headache			
Other*			

Statistical Analysis Plan

Safety Scoring Key	
Reaction	Point value
None	0
Local - if any marks in white boxes	1
Systemic mild (WAO Grade 1/2) - if any marks in green boxes	2
Systemic moderate (WAO Grade 3) - if any marks in yellow boxes	3
Systemic severe (WAO Grade 4) - if any marks in red boxes	4

Severity will be determined by study staff. Local reactions will be divided into: 1) mild: events require minimal or no treatment and do not interfere with the patient's daily activities; 2) moderate: events result in a low level of inconvenience or concern with the therapeutic measures. Moderate events may cause some interference with functioning; 3) severe: events interrupt a patient's usual daily activity and may require systemic drug therapy or other treatment. Severe events are usually incapacitating. Systemic reaction severity will be based on the World Allergy Organization grading for systemic allergic reactions (mild = grades 1/2, moderate = grade 3, severe = grade 4/5).

*Will be specified if unexpected, unlisted reaction occurs.

Statistical Analysis Plan

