## 7 STUDY INTERVENTION DISCONTINUATION AND PARTICIPANT DISCONTINUATION/WITHDRAWAL

### 7.1 DISCONTINUATION OF STUDY INTERVENTION

Participants may choose to discontinue ILIT treatment at any time without prejudice. Discontinuing participation in the study will not preclude patients from continuing alternate allergy treatments. Patients may choose to continue as a patient of TASC or seek treatment elsewhere at their own expense. Discontinuation of ILIT treatment does not mean discontinuation from the study, and remaining study procedures should be completed as indicated by the study protocol to ensure patient follow-up through the end of the allergy season. Reasonable efforts will be made to contact the patient to encourage orderly completion of study discontinuation procedures. If a clinically significant finding is identified (including, but not limited to new medical conditions, adverse effects, or worsening of symptoms) after enrollment, the investigator or qualified designee will determine if any change in clinical patient management is needed. New clinically relevant finding will be reported as an adverse event (AE). For patients that discontinue the study prior to the scheduled end-of-study visit, the reason for discontinuation will be collected.

The data to be collected at the time of discontinuation will include the following:

- Adverse events, concomitant medications, reasons for discontinuation, vital signs

ILIT treatment of subjects may be discontinued at any time by the investigator any at any time the investigator determine that it is clinically a clinical determination that it is in the interest of the patient to discontinue treatment.

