**14 APPENDIX 3 ASSESSMENT TOOLS AND RATING SCALES**

**Total Safety Score (TSS) Worksheet**

Subject ID:

Injection # (write in 1, 2, or 3):

RECORDING INSTRUCTIONS: Mark/code the box(es) indicating reactions experienced by this subject following injection (D = definitely related to study, P = probably related to study, N = not related to study)

ILIT protocol defined grading scale for severity# of adverse events			
	Mild	Moderate	Severe
LOCAL REACTIONS			
Lymph node swelling			
Itch			
Redness			
Other*			
SYSTEMIC REACTIONS			
Rhinorrhea			
Sneezing			
Dyspnea			
Cough			
Wheeze			
Pruritus			
Rash			
Angioedema			
Nausea			
Vomiting			
Diarrhea			
Headache			
Other*			

SCORING INSTUCTIONS: Give one score for most severe reaction (see scoring key on back) - min score 0, max score 4

SCORE for this injection	
---------------------------------	--

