10. SAFETY ANALYSIS

Safety analyses will compare treatment groups using appropriate methods according to their nominal or quantitative nature and will include descriptive statistics rather than formal hypothesis testing for noninferiority due to the small overall sample size. The study included a formal stopping rule in the event two systemic allergic reactions were detected.

The total safety score (TSS) and proportion of subjects with any treatment-emergent SAE, as defined in the composite safety endpoint, will be assessed using the Mann-Whitney test. Data will be presented in the form of descriptive statistics and appropriate tables and graphs with a conclusion on whether the significance level allowed the null hypothesis for each test to be rejected.

Safety Objective: To evaluate the safety profile of ILIT versus placebo using a standardized scoring system, the Total Safety Score worksheet, for AEs of interest (AEIs) up to 60 minutes post-procedure.

Statistical Analysis Plan

Safety Endpoints:

- Proportion of subjects experiencing a serious, treatment-emergent AE up to 60 minutes after an intranodal injection procedure
- Proportion of subjects experiencing systemic reactions to ILIT relative to placebo and severity of reactions relative to placebo as assessed by the Total Safety Score (TSS)
- Proportion of subjects reporting local injection site reactions relative to placebo and severity of local reactions relative to placebo, as assessed by the TSS

Additional safety tables and listings will include summaries of all patients experiencing anaphylaxis or treated with epinephrine, by group and a table of TSS reactions by severity by group.

Safety Population:

Safety analysis will include all participants who received at least one dose of study intervention regardless of whether they provided any diary data.

Calculation cumulative safety score (sum of TSS) across all patients by group will be performed in accordance with the scoring instruction described in section 7.4

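### The by-arm Total Safety Score is a sum with no denominator, so this descriptive total can be compared between arms only if patients and injections are equal

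*SAP*

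**What the plan says.** The Protocol's Appendix 3 worksheet gives one score per injection ("min score 0, max score 4"). SAP 7.4 then builds two further levels. At patient level: "A cumulative Safety Score for each patient will be calculated from the sum of the Safety Score at each visit". At group level: "The Total Safety Score for a treatment group will be the sum of the cumulate Safety Score for each patient in the assigned group". SAP 10 repeats the group total as an output: "Calculation cumulative safety score (sum of TSS) across all patients by group will be performed". No denominator appears in either section, and SAP section 1 gives SAP definitions precedence over the Protocol's.

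Patients can contribute different numbers of injections. On the safety population, SAP 10 states: "Safety analysis will include all participants who received at least one dose of study intervention". Protocol 7.1 allows early stopping: "Participants may choose to discontinue ILIT treatment at any time without prejudice". Protocol 7.2 does not replace dosed patients who leave. The SAP's data-handling entry on premature discontinuation (7.2) is marked as not applicable, so no rule covers an incomplete series.

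On inference, SAP 10 says that the safety analyses "will include descriptive statistics rather than formal hypothesis testing for noninferiority due to the small overall sample size". It nevertheless plans a test of the TSS together with the proportion with serious events, which, "as defined in the composite safety endpoint, will be assessed using the Mann-Whitney test".

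**The concern.** A sum over patients rises with the number of patients, and a sum over visits rises with the number of injections. If the arms differ in either, the two totals differ even when the reaction rates are the same. A real difference can also be masked if the arm with more reactions is smaller or less exposed. A reader who sees one total per arm in a safety table will naturally compare them.

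The naming adds to the problem. SAP 7.4 gives the name Total Safety Score to a single number per arm, while SAP 10 applies a rank test to the TSS. A rank test needs one value per patient, so the SAP does not say outright which variable is tested.

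The presentation matters because Protocol 9.4.2 places the efficacy analysis second to the comparison of safety between groups.

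**Working it through.** The documents state no expected value for the TSS. The only planning figure needed is the number of patients.

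**1. Arm sizes.** Protocol 9.2 and SAP 5.1 give 23 enrolled, with up to 16 per group. Protocol 5.4 gives a target of 32. The 23 reproduces: the overall F test of a regression with two predictors, f² = 0.50, noncentrality f² × N and two-sided alpha 0.05 has power 0.788 at N = 22 and 0.810 at N = 23. Plausible splits are therefore 16 v 16, or 12 v 11 as the closest split of 23. Protocol 6.3 specifies 1:1 allocation but describes no blocking, so wider splits are possible but assumed. Under simple randomisation of 23, ignoring the ceiling of 16, the chance of a difference of 5 or more is 0.41.

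**2. Effect of arm size.** If all injections are given, expected group sum = n × mean per patient. With the same mean in both arms, the ratio of sums is n1/n2:
- 16 v 16: 16/16 = 1.00
- 12 v 11: 12/11 = 1.09
- 14 v 9 (assumed): 14/9 = 1.56

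For scale, Protocol 2.2 reports a mean TSS of 0.6 on active treatment in the earlier US trial. At 12 v 11 that gives 12 × 0.6 = 7.2 against 11 × 0.6 = 6.6, a gap of 0.6 points.

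**3. Masking by arm size.** With an assumed 9 ILIT and 14 placebo patients, sums are equal when the ILIT mean is 14/9 = 1.56 times the placebo mean. For example, 9 × 0.84 = 14 × 0.54 = 7.56.

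**4. Effect of injections given.** With a constant mean per injection, expected group sum = injections given × mean per injection. Twelve patients with full series receive 12 × 3 = 36. If 4 stop after the first (assumed), 36 − 4 × 2 = 28 are given, and the expected sum falls to 28/36 = 0.78 of its full value. A per-injection mean 36/28 = 1.29 times higher would then give the same expected sum as a full arm of 12.

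**5. Simulation with no true difference.** Assumed probabilities per injection were 0.85, 0.12 and 0.03 for scores 0, 1 and 2. The mean is 0.12 × 1 + 0.03 × 2 = 0.18 per injection, or 0.54 per patient. All three injections were given, in 6,000 runs. At 14 v 9:
- average sums were 7.6 v 4.9, and the larger arm had the higher sum in 72% of runs and the lower in 20%;
- average means were 0.540 v 0.542 per patient and 0.180 v 0.181 per injection.

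The Mann-Whitney test on patient-level cumulative scores rejected in 4.8% of runs at 12 v 11, 4.2% at 14 v 9 and 5.1% at 16 v 16. Arm size does not inflate its error rate. These runs included no early stopping, so they say nothing about incomplete series.

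**The case against.** The group total is not one of the listed safety endpoints. Those are proportions of subjects with serious events, systemic reactions and local reactions, with severity. They have denominators, and SAP 10 also plans a table of reactions by severity. A rank test can only run on patient-level values, and there arm size does no harm. The patient-level sum is also legitimate: Protocol 2.2 describes the earlier US trial as summing injection scores within each participant. With near-equal arms and complete series, the distortion is between 0 and 9%. All of this stands, and it confines the point to one descriptive total.

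A reader might go further and infer that early stopping makes the arm with more reactions look safer in the formal comparison. The documents do not support that. A patient who scores 4 at the first injection and stops keeps a cumulative score of 4, against a cited active-arm mean of 0.6. That patient would still rank near the top and counts in full among systemic reactors and in the severity table. What is lost is any score from later injections, so the cumulative score is lower than or equal to what a full series would have given. The size of that loss is unknown, because the documents give no stopping counts.

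The objection does not remove the group total itself. SAP 7.4 and 10 both prescribe it, neither supplies a denominator, and 7.4 gives it the tested variable's name.

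**Conclusion.** The point holds for the descriptive by-arm total. As defined, it is not comparable between arms unless both the number of patients and the number of injections are equal. The ratio with no true difference is 1.00 at 16 v 16 and 1.09 at 12 v 11. The 1.56 at 14 v 9 rests on an assumed split, and the 0.78 on an assumed 4 of 12 stopping after one injection.

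It does not follow that the trial's safety comparison as a whole is unsound, or that the patient-level cumulative score is wrong. The proportions and the severity table are unaffected. A patient-level Mann-Whitney test is unaffected by arm size; its remaining weakness is that a cumulative score omits injections not given, and the SAP is silent on this. The correction is modest but worth making, because the present rule yields a summary that invites a comparison it cannot support.

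**What to change.** In SAP 7.4 and 10:
- Define the TSS at patient level, as the sum over that patient's injections, in line with the cited US trial.
- Replace the group sum with the mean or median and the distribution per patient, and the mean per injection given, by arm, with the numbers of patients and injections beside them. The per-patient mean removes the effect of arm size only; the per-injection mean also accounts for the number of injections given.
- State that the Mann-Whitney test uses the patient-level cumulative score.
- Add the worst score per patient as a supportive summary, for patients with fewer than three injections. It should not replace the cumulative score, since it ignores repeated reactions.

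The cost is a change of SAP wording and a little extra tabulation. The per-injection worksheets already hold the data.
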